7.0 Consent Process

This study will use the procedures described below to obtain informed consent for study participation.

Electronic Health Record Data Abstraction. A full waiver of HIPAA Authorization is requested to generate the EHR query that will be used to establish the list of patients who are potentially eligible to participate in the study and to obtain other personal health identifiers (e.g., MRN, names, address, telephone numbers) for sending invitation letters and conducting recruitment calls. The waiver of HIPAA Authorization will also include permission to abstract clinical (e.g., co-morbidities, medications, vital signs) and socioeconomic data (e.g. insurance type, race/ethnicity), and to utilize text algorithms developed by BMIC to abstract information from clinical notes relating to smoking status. Clinical and sociodemographic data abstracted from the EHR will be included in de-identified datasets for analysis of study outcomes relating to factors (i.e. zipcode, co-morbidities) associated with smoking behaviors, stress responses, and enrollment and retention . The outcomes rendered from the EHR data that is obtained will help to inform future studies that further address disparities relating to lung cancer risk.

All PHI data will be collected at the time of screening. No further data collection occurs on these participants following screening and EHR abstraction under the full waiver. Further data collection for participants who choose to enroll will be covered under the partial waiver for the baseline interview, and the signed informed consent form and HIPAA if they choose to participate further in the study.

Screening Interview and Baseline Survey. A waiver of written informed consent/partial waiver of signature element is requested to complete the screening interview and baseline survey. Patients will be read a statement of study information before obtaining verbal consent. Once verbal consent is achieved, the screening interview will be completed by telephone. Baseline surveys will be completed according to the participant's preference either by telephone or through self-administration via a redcap survey weblink.

Laboratory Visits and Biorepository Biospecimen Donation. This study will involve laboratory visits for biospecimen collection and stress assessments, followed by at-home saliva collections at two follow-up timepoints (see section 8.0 for detailed methods). Written informed consent will be obtained at the Pre-Challenge laboratory visit (1st laboratory visit) prior to the initiation of any study activities. The written informed consent will include permission to collect biospecimens (e.g. urine, saliva), completion of a social stress test, perform at-home saliva collection and smoking assessment following the laboratory visits, and to use data on exposure to chronic, psychosocial, and structural stressors obtained during the study. The informed consent will also include an option for participants to donate biospecimens to the TRACER Biorepository located at VCU. If consent for biospecimens and data is provided, this information will be processed and stored using the procedures described in study design and methods. Provision of consent for biospecimens and data among individuals who do not meet final eligibility determination will be recorded in the data management system.

To obtain written informed consent, the research assistant (RA) will meet participants in a private room to review the informed consent form (ICF) and answer questions about the procedures involved in participating in the study, describe the voluntary nature of study participation, and discuss procedures for withdrawing. Following the informed consent discussion, participants will immediately be asked to sign the ICF, the RA will also sign and date the ICF, and a copy of the signed ICF will be provided to participants. The original ICF will be filed in the participants study chart and stored in a locked file cabinet. The RA will also complete an informed consenting process documentation form that contains a checklist for the RA to adhere to while conducting the informed consenting process. This form will also be filed in the participant's chart.

8.0 Study Design / Methods

This research is a prospective observational study that will measure acute and chronic stress responses among African American and white smokers. Acute stress responses will be measured following exposure to a validated laboratory social stress test and chronic stress responses will be measured at 4- and 8-weeks following the laboratory stress test using at home collection. The procedures described below will be completed.

Screening Interview and Baseline Assessment. A 30-minute telephone interview will be conducted by research assistants from MUSC to screen participants for initial eligibility and those who are eligible will be invited to enroll into the study and complete a baseline survey. Participants that agree to enroll into the study, will be given the option to participate in the baseline survey over the telephone or through self-administration via a redcap survey link. The baseline survey will obtain information relating to sociodemographic characteristics and measure exposure to chronic economic stressors (e.g., low income, financial strain), psychosocial stressors (e.g., perceived stress, social isolation), exposure to structural stressors (e.g., violence, crime), and community perceptions and resources (e.g., collective efficacy). Additionally, other factors relating to smoking history, nicotine dependence, and reasons for smoking will also be measured, along with perceived risk and control over developing lung cancer, utilization of lung cancer screening, and interest in quitting smoking will also be measured during the baseline assessment. Zip code and street address will be confirmed as part of the telephone interview to mail financial incentives and send study reminders. Once participants completed the baseline survey, they will be invited to participate in the laboratory assessments described below.

Laboratory Visits. This study will involve four laboratory visits that will include a pre-challenge visit (lab visit 1) to collect biospecimens, a stress exposure visit (lab visit 2) that will involve conducting the Trier Social Stress Test (TSST), and two visits (lab visits 3 and 4) at 4- and 8-weeks after the TSST visit to collect final saliva samples. Each visit is explained in more detail below.

Pre-Challenge Visit. Following completion of the screening interview and baseline survey, participants will complete a pre-challenge visit to obtain urine samples that will be used to determine final eligibility. The pre-challenge visit will be completed at the Research Nexus Lab at MUSC. Participants will be asked to smoke as usual prior to the pre-challenge visit but to not eat or drink one hour before the session. During the Pre-Challenge Visit, screening tests will determine final eligibility, these include urine toxicology; individuals whose results indicate current substance abuse (e.g., cocaine) will be excluded (not eligible for further participation). Saliva samples will also be obtained during the pre-challenge visit to determine cortisol and cotinine levels using established salivary swab collection methods and validated thresholds. To further evaluate and confirm active smoking behaviors, a breath monitor will be used to measure levels of carbon monoxide in the blood. The MINI International Neuropsychiatric Interview (MINI) will be administered by a trained research technician to evaluate mental status and psychiatry exclusion criteria. Participants will be excluded from participation in the laboratory stress visit if they meet the exclusion criteria (e.g., positive responses on the MINI, or positive toxicology result). Participants eligible following pre-challenge visit will be scheduled for the stress exposure visit described below.

TSST Stress Exposure Visit. The stress exposure visit will be completed within 72-hours of completing the pre-challenge visit. As with the pre-challenge visit, participants will be instructed to smoke as usual, but not to eat or drink during 1-hour prior to stress exposure visit. The number and brand of cigarettes smoked prior to the TSST will be recorded. Participants will be asked to smoke a single cigarette of their usual brand prior to initiating the stress test to standardize the time since last smoking. Fifteen minutes later, baseline clinical and subjective measures will be obtained. Clinical measurements will include heart rate and blood pressure using a standardized monitor, and saliva collection using a Salivette. Following collection of these baseline measures, participants will be escorted back to their room to start the TSST. The TSST is a standardized psychological stress challenge that has been validated and used extensively in research studies; a meta-analysis supports that it is the gold standard for evoking an HPA-axis stress response in a laboratory setting. The TSST (see **TSST Procedures and Timeline**) will be administered in

the Research Nexus Lab. Outcome measures (e.g., cortisol responses) will be collected prospectively during the stress exposure visit. Heart rate variability (HRV) and blood pressure will also be measured using standard medical equipment and procedures during the TSST. Cigarette craving and smoking behavior will be measured after the TSST has been completed. Specifically, smokers will rate their urge to smoke immediately after the last saliva sample has been taken as part of the TSST. After completing this self-report measure, they will be given the opportunity to smoke a cigarette using a pocket CReSS system that measures and records smoking topography (Puff #, Volume, IPI). Smoking behavior (smoke versus not smoke) will be recorded in the participant's study chart and stored in study's data management Redcap system.

TSST Procedures and Timeline		
TIME	EXPERIMENTAL PROCEDURE	STRESS ASSESSMENT
3:00pm	Acclimation period (15 minute duration)	Patient arrives and given relaxation tools (i.e. spa video, magazine, nature scenes)
Baseline (immediately following acclimation period)	Stress measurements	Take cortisol, BP, HR, and assess SUD
Immediately before TSST (12 minutes following baseline)	Stress measurements	Take cortisol, BP, HR, assess SUD, and explain the task and give participant paper to write notes
3:33- 3:44	TSST	
5	Interview task	
5	Arithmetic task	
Post TSST stress assessments (12 minute increments)		
Post TSST (2 minutes following TSST)	Post-TSST Assessment	Cortisol, BP, HR, SUD
12 mins post TSST	Post-TSST Assessment	Cortisol, BP, HR, SUD
24 mins post TSST	Final Post-TSST Assessment	Cortisol, BP, HR, SUD

Post-Stress Test Saliva Collection. At the end of the TSST, participants will be given saliva kits (Salimetrics oral swab) to collect samples at home 4- and 8-weeks after the stress exposure visit. Self-reported data on perceived stress and life experiences during the past month will also be obtained using validated instruments. Standard collection procedures (e.g., avoid eating/drinking/brushing teeth within 1-hour of sample collection; do not engage in vigorous physical activity; no alcohol within 12-hours of sample collection) will be provided to participants as an instructional sheet. Saliva will be collected at fixed intervals (upon waking, 30-minutes after waking, 4:00 pm, and 6:30 pm). The final 6:30pm saliva collection will occur at the Nexus Laboratory and participants will be instructed to return their other collected samples from home at this time. Collection dates will be based on the date the stress exposure visit was completed and sample collection procedures will be explained verbally and in writing at the end of the stress exposure visit. Participants will be given an instructional sheet for how to perform the sample collections. Participants will also be given a collection log to record the date and time of each collection, the number and brand of cigarettes smoked on the collection day, quit attempts, the amount of stress experienced during the past month, and positive and negative life experiences during the past month. Participants will be contacted the night before the collection date by telephone, email, and text to remind them about the sample collection date, collection and storage procedures, and the information that should be recorded in the sample collection log. Saliva samples will be collected at 4- and 8-weeks after the TSST to be consistent with the collection timepoints used in previous research with African American and white treatment-seeking smokers.

9.0 Data Collection and Storage.

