1.0 Objectives / Specific Aims

This study will examine racial differences in stress responses between African American and white male smokers as part of the Translational Research Center in Lung Cancer Disparities (TRACER).

- **Aim 1: Examine racial differences in acute physiological stress responses between African American and white male smokers using a laboratory model. The association between acute physiological stress response and tobacco-related behaviors will also be evaluated.**

Hypotheses: African American smokers will be more likely than white smokers to have a blunted cortisol response to an acute laboratory stressor. African American smokers will also have significantly greater cigarette craving and be more likely to smoke following exposure to an acute physiological stressor compared to white smokers following an acute laboratory stressor.

- **Aim 2: Evaluate racial differences in daily cortisol patterns between African American and white male smokers.**

Hypotheses: African American smokers will be more likely than white smokers to have blunted daily diurnal cortisol slopes. Compared to white smokers, African American smokers will have lower absolute cortisol values during the waking day.

- **Aim 3: Identify factors that are important to acute and daily stress responses among African American and white male smokers by examining acute and daily cortisol patterns based on exposure to chronic stressors.**

Hypotheses: Acute and daily cortisol responses will be associated with chronic stressors such that men who have greater exposure to SES, structural, and psychosocial stressors will have blunted acute and daily cortisol patterns. The relationship between acute and daily cortisol patterns, nicotine metabolism, and nicotine dependence will also be explored among African American and white male smokers as part of this aim.

- **Aim 4: Examine social and clinical factors associated with study enrollment and retention.**

Hypotheses: Those with greater comorbidities and social issues (i.e. lower SES, education, social support) will have lower rates of study enrollment and retention compared to those with fewer comorbidities and social issues.

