Aim 1: Examine racial differences in acute physiological stress responses between AA/Black and white male smokers using a laboratory model. The association between acute physiological stress response and tobacco-related behaviors will also be evaluated. *Hypotheses:* AA/Black smokers will be more likely than white smokers to have a blunted cortisol response to an acute laboratory stressor. AA/Black smokers will have lower absolute cortisol values during the acute stressor compared to white smokers. AA/Black smokers will have significantly greater cigarette craving and be more likely to smoke following exposure to an acute physiological stressor compared to white smokers following an acute laboratory stressor.

Sample Size and Power Calculations: This aim will examine racial disparities in cortisol responses to an acute stressor among AA/Black and white male smokers in a laboratory setting. Changes in cortisol levels will be the primary outcome variable and will be measured multiple times during the course of the TSST. A sample size of 50 AA/Black (Mean DCS=0.20, SD=0.20) and 50 white (Mean DCS=0.35, SD=0.30) males achieves 84% power to detect a difference of 0.15 μ g/dL between the 2 groups with a significance level of 0.05 using a two-sided two-sample *t*-test. This sample size would also provide 80% power to detect a difference of 0.14 μ g/dL in absolute cortisol value between AA/Black (mean=0.17, SD=0.19) and white (mean=0.31, SD=0.30) males with a significance level of 0.05 using a two-sided two-sample *t*-test.

Statistical Analysis: First, descriptive statistics will be generated to characterize enrollment outcomes using clinical data (e.g., co-morbidities, age, etc) obtained from the EHR during the recruitment process. Statistical analyses will compare enrollees vs. decliners in terms of race, clinical factors, and smoking history to identify variables that should be controlled for in the analysis of stress reactivity and smoking behaviors.

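### As written, urge to smoke is rated only after the TSST, so a racial difference in craving cannot be attributed to the stressor

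*Combined protocol and SAP*

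**What the plan says.** Section 1.0 (Aim 1) predicts that "African American smokers will also have significantly greater cigarette craving and be more likely to smoke following exposure to an acute physiological stressor", compared with white smokers. Section 10.1 (Aim 1) repeats the prediction.

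Section 8.0 (TSST Stress Exposure Visit) gives the timing: "Cigarette craving and smoking behavior will be measured after the TSST has been completed". More exactly, "smokers will rate their urge to smoke immediately after the last saliva sample has been taken as part of the TSST", and the chance to smoke follows the rating.

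Before the stressor, each man smokes one cigarette of his usual brand so that time since last smoking is standardized. Then, "Fifteen minutes later, baseline clinical and subjective measures will be obtained". The text goes on to list the clinical measures (heart rate, blood pressure, saliva) but does not say what the subjective ones are. The baseline row of the TSST timeline reads "Take cortisol, BP, HR, and assess SUD". The same four items recur at every later assessment, up to the row headed "Final Post-TSST Assessment", 24 minutes after the TSST.

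The baseline survey and the Pre-Challenge Visit name no craving scale, and no non-stress session is described. Section 10.1 (Aim 1) models craving scores and the proportion who smoke with regressions on race, similar to the rAUC model, adjusted for known and potential confounders. Nicotine metabolism is the example given. No pre-stress craving term is named. Cortisol, by contrast, has its baseline subtracted in the rAUC.

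**The concern.** A single rating after the stressor is the sum of at least three things: the man's usual craving, the craving that has returned since the standardizing cigarette, and any craving provoked by the TSST. Only the third is a response to stress. Nothing in a comparison of two pre-existing groups makes the first two equal, so a racial difference in ordinary craving would look the same as a racial difference in stress-induced craving. The plan deals with this problem for cortisol but not for craving, which belongs to the same aim. The smoke/not-smoke outcome has the same weakness. What is at stake is the interpretation of one Aim 1 hypothesis. The rating also cannot be recovered once a visit is over.

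**Working it through.** **No figure to reproduce.** The documents give no mean, SD, effect size or power for craving. The calculations below illustrate size under stated assumptions.

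**Inputs.** From the plan: 50 men per group (section 5.0), and two-sided alpha of 0.05 with a two-sample t-test (section 10.1, stated for cortisol and assumed here for craving). Assumed: craving SD of 1 within each group at both times; a usual-craving gap g of 0.2 to 0.4 SD; a pre-post correlation r of 0.5, 0.6 or 0.7. Results come from the noncentral t distribution.

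**1. Post-only comparison, no differential stress effect.** Noncentrality = g / √(2/50) = g / 0.2, with 98 degrees of freedom.

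| Gap g (SD) | Noncentrality | Chance of a significant result |
|---|---|---|
| 0 | 0 | 5% |
| 0.2 | 1.0 | 17% |
| 0.3 | 1.5 | 32% |
| 0.4 | 2.0 | 51% |

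This test is unadjusted, so g should be read as the gap left after the planned covariates.

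**2. With a pre-TSST rating: a stable 0.4 SD gap, no differential stress effect.**

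- Change from baseline: the gap is in both ratings and cancels (0.4 − 0.4 = 0), so rejection returns to 5%.
- Baseline as covariate: the gap left is 0.4 × (1 − r), the residual SD is √(1 − r²), and the standard error is √(1 − r²) × √(2/50 + 0.4²/98), since the groups differ on the covariate. The last factor is √0.0416 = 0.204.

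| r | Gap left (SD) | Noncentrality | Rejection, covariate analysis |
|---|---|---|---|
| 0.5 | 0.20 | 0.20 / (0.866 × 0.204) = 1.13 | 20% |
| 0.6 | 0.16 | 0.16 / (0.800 × 0.204) = 0.98 | 16% |
| 0.7 | 0.12 | 0.12 / (0.714 × 0.204) = 0.82 | 13% |

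**3. Power for a true 0.4 SD differential stress effect, no usual-craving gap.** Post-only: noncentrality 0.4 / 0.2 = 2.0, power 51%. Change: SD = √(2(1 − r)). Covariate: SD = √(1 − r²).

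| r | SD of change | Power, change | Residual SD, covariate | Power, covariate |
|---|---|---|---|---|
| 0.5 | 1.000 | 51% | 0.866 | 63% |
| 0.6 | 0.894 | 60% | 0.800 | 70% |
| 0.7 | 0.775 | 72% | 0.714 | 79% |

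The two analyses therefore do different jobs. Change removes a constant gap but gains no power at r = 0.5. The covariate analysis has more power but leaves part of the gap.

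**4. Time since the cigarette.** Baseline measures come 15 minutes after it. If it is smoked near 3:00 pm (an assumption), the TSST ends at 3:44 and the last sample is 24 minutes later, at 4:08. The urge rating is then about 68 minutes after the cigarette, and about 68 − 15 = 53 minutes after the baseline measures.

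**The case against.** **The hypothesis is about craving after exposure, not an increase in craving.** This stands. A post-TSST comparison answers that wording. It does not support reading the difference as a response to the stressor, which is what Aim 1 sets out to study.

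**Urge may already be among the baseline subjective measures.** This stands in part. A reader might infer that the plan definitely takes no pre-stress urge rating, but the documents do not settle that. The subjective measures are unnamed, and the timeline's silence proves little, since it also omits the post-TSST urge rating, the smoking-topography session and heart rate variability. Still, the text expressly places craving after the TSST, so post-only is the more natural reading. Even if a pre-rating exists, section 10.1 names no use for it.

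**The plan already has controls.** It standardizes time since last smoking, records cigarettes smoked beforehand, measures dependence and smoking history, and adjusts for confounders. These reduce a difference in usual craving but do not remove it, because none measures a man's craving before the stressor. They are the reason the illustrated gap must be read as a residual one.

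**A pre-rating is only a partial cure.** This stands. With no non-stress session, a group difference in how fast craving returns after the cigarette would still resemble a stress response.

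**Conclusion.** The point holds as a limit on attribution. As the plan reads, a racial difference in post-TSST craving can be reported, but it cannot be ascribed to the stressor. Under the assumptions above, a residual usual-craving gap of 0.2 to 0.4 SD would produce a significant post-only result in 17% to 51% of studies with no differential stress effect. The size of any such gap is unknown from the documents.

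Two stronger readings should be resisted. One is that a pre-stress rating would, in any single analysis, both remove the gap and lift power to 63–79%. Those power figures belong to the covariate analysis, which still rejects in 20%, 16% or 13% of studies for a stable 0.4 SD gap. The change analysis, which removes the gap, has power of 51%, 60% or 72%. The other is that this undermines Aim 1's primary comparison. It does not: section 10.1 names cortisol change as the primary outcome, and the rAUC is baseline-corrected.

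The change is worth making because it is cheap, but the matter is secondary.

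**What to change.** 1. In section 8.0 and the TSST timeline, add the same urge-to-smoke item at the pre-TSST baseline, alongside SUD, or state that the baseline subjective measures already include it.
2. In section 10.1 (Aim 1), prespecify change in urge from baseline as the primary craving analysis; with two ratings this is the race-by-time term. Baseline as covariate can be a sensitivity analysis, with a note that it leaves part of any usual-craving gap. The two can disagree when groups are not randomized, so the choice should be fixed before the data are seen.
3. Keep the post-only comparison as descriptive.
4. Include pre-TSST urge in the smoke/not-smoke model.
5. State as a limitation that, without a non-stress session, group differences in the return of craving since the standardizing cigarette remain mixed with stress-induced craving.

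The cost is one short self-report item at an existing assessment, a small amendment and a few sentences of analysis text. Asking about urge before the task might slightly prime craving, and the documents give no basis for assuming that this would be equal in both groups. Men who have already completed the visit would have no pre-rating, so an early change is better than a late one.
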